10.7 Rescue Therapy

Rescue therapy with a VEGF inhibitor can be administered to any study subject who experiences a significant decrease in BCVA, defined as BCVA loss of >7 letters from baseline (Visit 1 – Screening/Randomization), accompanied by an increase in OCT center subfield thickness of >75 μ m as compared to the previous study visit, as assessed by the Investigator. The OCT images completed during the assessment for rescue therapy initiation should also be uploaded to the central reading center.

Therapies can include:

- Avastin (bevacizumab), or
- Lucentis (ranibizumab), or
- Eylea (aflibercept), or
- Macugen (pegaptanib)

Note: Steroid and focal laser photocoagulation rescue is not permitted during the study.

Subjects who discontinue IP and are started on rescue therapy should continue with the visit schedule and assessments through the end of the study.

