11.0 ANALYSIS PLAN

11.1 Analysis Data Sets

The primary analysis population will be the Per Protocol (PP) population, defined as all subjects who were randomized, completed the study as planned (i.e., after 28-day on-treatment period and 28-day follow-up period), and did not have significant protocol deviations. Protocol deviations will be reviewed by the study team and assessed for importance (i.e., the potential exclusion of a subject) prior to database lock.

The modified intent-to-treat (ITT) population will include subjects who were randomized and completed at least 1 on-IP study visit. The safety analysis set will include all randomized subjects.

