11.4 Discontinued Subjects

Discontinued subjects will not be replaced. If a subject requires discontinuation of IP and placement on rescue therapy, that subject should be continued in the study and followed through the end of the study.

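### Rescued subjects are followed to Day 56, but the analysis sections take no account of anti-VEGF rescue, so arm means may flatter SF0166

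*Combined protocol and SAP*

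**What the plan says.** **Rescue (10.7).** A VEGF inhibitor may be given when two conditions hold together. One is a vision criterion, "defined as BCVA loss of >7 letters from baseline". The other is a CST rise of more than 75 µm "as compared to the previous study visit, as assessed by the Investigator". On what follows, the section says: "Subjects who discontinue IP and are started on rescue therapy should continue with the visit schedule and assessments through the end of the study".

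**Follow-up (11.4).** The same instruction is given for the case described as "If a subject requires discontinuation of IP and placement on rescue therapy". It concerns follow-up only and gives no rule for the data.

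**Analysis sets (11.1).** "The primary analysis population will be the Per Protocol (PP) population". Members must have "completed the study as planned (i.e., after 28-day on-treatment period and 28-day follow-up period), and did not have significant protocol deviations". On deviations: "Protocol deviations will be reviewed by the study team and assessed for importance", before database lock. The modified ITT "population will include subjects who were randomized and completed at least 1 on-IP study visit". None of these definitions mentions rescue.

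**Outcomes (11.3).** The primary outcome is mean change in CST and macular volume from the reading center, and the secondary is mean change in BCVA. Both are summarized descriptively. No visit is named, and nothing is said about values obtained after rescue.

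**Schedule (2.0).** OCT and BCVA are taken at all five visits. Dosing ends at Day 28, so Day 42 and Day 56 are off treatment.

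**The concern.** Keeping rescued subjects under observation is sound. The difficulty is what the analysis then does with them. Rescue picks out subjects who are getting worse. If their later values count as change on SF0166, the arm is credited with whatever the anti-VEGF agent achieved. If they leave the primary set, the arm loses its failures. Both tend to favor SF0166, and more so in the arm with more rescue.

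The descriptive arm means are the whole efficacy result of this trial. Its readers will use them to judge each dose and to compare the two doses.

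**Working it through.** **Step 1. Follow a rescued subject through the written rules, by timing of rescue.**

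| Rescue | PP (primary) | mITT |
|---|---|---|
| Before Day 28, IP stopped | Likely out: the 28-day treatment period was not completed | Stays in; post-rescue values enter every later visit mean, including Day 28 |
| At or after the Day 28 assessment | Can stay in; Day 42 and/or Day 56 means include post-rescue values; Day 14 and Day 28 are untouched | Same as PP |

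Section 10.7 does not say that rescue always means stopping IP. A subject rescued early who continued IP could therefore remain in PP and affect its Day 28 mean. That case rests on silence alone, and 11.4 pairs rescue with stopping.

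**Step 2. Weight of one subject.** The plan gives no figure for rescue, so there is none to reproduce. Planned arm size is 20 (synopsis; 2 × 20 = 40). Section 8.0 allows for at least 30 completers; an equal split, which is an assumption, gives 15 per arm.

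- n = 20: 1/20 = 5% of the arm mean
- n = 15: 1/15 = 6.7%

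**Step 3. What the trigger fixes.** With whole-letter scores, a loss of more than 7 is at least 8 letters at the rescue assessment. CST, on the Investigator's read, is more than 75 µm above the previous visit. Both statements describe that one assessment.

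**Step 4. Illustration for CST.** Every input except n = 20 is assumed. Let k be the number rescued, m = -30 µm the mean change of the others, r = +80 µm the change from baseline at the rescue assessment, and p = -20 µm the change at a later visit.

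- Observed = [(n - k)m + kp]/n
- Carried = [(n - k)m + kr]/n
- Excluded = m

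For n = 20, k = 3:

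- Observed: (17 × -30 + 3 × -20)/20 = -570/20 = -28.5 µm
- Carried: (17 × -30 + 3 × 80)/20 = -270/20 = -13.5 µm
- Excluded: -30.0 µm

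| n | k | Observed | Carried | Excluded |
|---|---|---|---|---|
| 20 | 1 | -29.5 | -24.5 | -30.0 |
| 20 | 2 | -29.0 | -19.0 | -30.0 |
| 20 | 3 | -28.5 | -13.5 | -30.0 |
| 15 | 1 | -29.3 | -22.7 | -30.0 |
| 15 | 2 | -28.7 | -15.3 | -30.0 |
| 15 | 3 | -28.0 | -8.0 | -30.0 |

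The gap between carried and observed is k(r - p)/n. Here r - p = 100 µm, so it is 5.0 µm per rescued subject at n = 20 and 6.7 µm at n = 15.

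**The case against.** The strongest reply is that the trial is exploratory, tests no hypothesis and reports descriptive statistics. The double trigger may make rescue rare. A summary of all observed mITT data is a legitimate choice. PP wording already points to excluding subjects who stop IP early, and a deviation review before lock is planned. In the illustration, observed and excluded differ by only 1.5 µm with three rescues at n = 20; the large gap comes from carrying the rescue value forward, which is itself a convention.

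Much of this stands. Type I error and power are not at issue, and the size cannot be estimated. But the planned review has no criterion for rescue, and the closeness of observed and excluded is no comfort: one absorbs the anti-VEGF response and the other removes the failure.

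Four stronger readings are tempting but not supported:

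- **The trigger sets a minimum bias.** One might divide 8 letters or 75 µm by the arm size and call it a floor (8/20 = 0.40 letters; 75/20 = 3.75 µm). That would need rescue at the scheduled visit being summarized and a zero mean change in the others. For CST it would also need a rescue at Day 14 with no OCT since Visit 1, and it would hold only for Investigator reads. The primary outcome uses reading-center values, and post-rescue values have no floor.
- **Observed and carried values bracket the truth.** They do not. Without rescue a subject might recover or worsen further.
- **9.3.2 makes rescue a protocol deviation.** Its heading says the listed treatments are barred during the study, and the list includes the four rescue agents. But the entries are pre-enrollment intervals and 10.7 is a specific provision. This is a wording conflict to reconcile, and a minor one.
- **A vehicle arm would have exposed the problem.** Rescue records show which values follow rescue; a control arm would not.

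**Conclusion.** The concern holds and should be settled before database lock. The direction is probably favorable to SF0166, because rescue selects worsening subjects; this assumes that anti-VEGF improves, on average, on the untreated course. For the end-of-treatment reading at Day 28, the exposure is rescue before Day 28: through mITT values, and through loss of subjects from PP. For Day 42 and Day 56 it is rescue at any time, including subjects who remain in PP.

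The magnitude is unknown. The firm figures are the weights: 5% of an arm mean per subject at n = 20, and 6.7% at n = 15 if 30 completers split equally. The CST illustration shows only that the unwritten choice can matter: -28.5, -13.5 or -30.0 µm from the same three rescued subjects. It is neither an estimate nor a range for the trial. What is affected is the reading of each dose, not a formal test.

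**What to change.** This changes analysis text only and leaves the rescue rule as it is.

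1. In 11.3, for study-eye CST, macular volume and BCVA by arm and visit, present two versions side by side: all observed values, and the rescue-assessment value carried to later visits (the reading-center value for OCT). Do this for mITT and for any rescued subject who remains in PP.
2. Show the mITT summary, with early-rescued subjects kept in, next to the primary PP summary. Do not rely on exclusion of rescued subjects or of post-rescue values alone.
3. Key the rule to anti-VEGF given in the study eye, since 9.3.1 permits injections in the non-study eye.
4. Report by arm the number of rescues before Day 28 and at or after Day 28, and whether IP was stopped. Label Day 28 (end of treatment) separately from Day 42 and Day 56 (off treatment).
5. Minor: reconcile the 9.3.2 heading with 10.7, and state in 11.1 how the pre-lock review classifies rescued subjects for PP.

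**Cost.** A few sentences and one or two tables. No new visits are needed: 10.7 already sends the rescue OCT to the reading center, and concomitant medications are collected at every visit. The sponsor should confirm that the injected eye is recorded, which the documents do not state. The carried-forward figure may be less favorable, and it assumes neither recovery nor further worsening without rescue, which is why the observed values belong beside it.

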11.0 ANALYSIS PLAN

11.1 Analysis Data Sets

The primary analysis population will be the Per Protocol (PP) population, defined as all subjects who were randomized, completed the study as planned (i.e., after 28-day on-treatment period and 28-day follow-up period), and did not have significant protocol deviations. Protocol deviations will be reviewed by the study team and assessed for importance (i.e., the potential exclusion of a subject) prior to database lock.

The modified intent-to-treat (ITT) population will include subjects who were randomized and completed at least 1 on-IP study visit. The safety analysis set will include all randomized subjects.

11.2 Demographic and Baseline Characteristics

Descriptive statistics will be used to tabulate and summarize study outcomes. Background and demographic characteristics will be presented.

11.3 Efficacy Analyses

11.3.1 Primary Efficacy

The primary efficacy outcome is the mean change in anatomic center subfield thickness and macular volume, measured by OCT. All OCT images will be read by the Investigator and a central reading facility. The primary efficacy outcome is determined by the OCT assessments from the reading center. The Investigator assessed OCT values will be analyzed for informational purposes.

11.3.1.1 Statistical Hypotheses

Not applicable, as no formal hypothesis testing is planned.

11.3.1.2 Analysis Methods

Both the Investigator assessed OCT values and the centrally read OCT values will be collected and analyzed. Descriptive statistics will be used to summarize the study outcomes. Continuous variables will be summarized by descriptive statistics (sample size, mean and standard deviation, median, minimum and maximum). Discrete variables will be summarized by frequencies and percentages. Any statistical tests performed to explore the data will be used only to highlight any interesting comparisons that may warrant further consideration.

11.3.2 Secondary Efficacy

The secondary efficacy outcome is the mean change from baseline in BCVA.

11.3.2.1 Statistical Hypotheses

Not applicable, as no formal hypothesis testing is planned.

11.3.2.2 Analysis Methods

Descriptive statistics will be used to summarize the study outcomes. Continuous variables will be summarized by descriptive statistics (sample size, mean and standard deviation, median, minimum and maximum). Discrete variables will be summarized by frequencies and percentages. Any statistical tests performed to explore the data will be used only to highlight any interesting comparisons that may warrant further consideration.

11.3.3 Supportive Efficacy

Not applicable.

11.3.4 Safety Analysis

Safety parameters to be evaluated include BCVA, slit-lamp and fundus findings, IOP and AEs. Adverse events will be summarized by presenting the number and percentage of subjects having any adverse event. Any other information collected (such as severity or relationship to investigational product) will be listed as appropriate.

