9.2 Usage

If a subject meets inclusion/exclusion criteria at Visit 1, the site will enter the required data into the IWRS in order to randomize the subject to a treatment arm. After subjects are randomized, they are dispensed SF0166 in 1 of 2 dose groups. The subject will use SF0166 BID for 28 days (1 drop in the study eye). If a subject qualifies in both eyes, SF0166 may be administered to both eyes (study eye and non-study eye) at the discretion of the Investigator. The study eye is defined as the eye with the worse BCVA at baseline (Visit 1 - Screening/Randomization).

At Visit 1, the site staff will dispense 1 carton (3 bottles) from the subject kit. At Visit 2, the site staff will collect the used IP bottles, and dispense an additional carton (3 bottles) from the kit. It is expected that subjects will use 2 bottles between each visit. The additional 3rd bottle in each carton is a back-up supply. If a subject requires a re-supply for any reason, an unscheduled re-supply can be completed through the IWRS.

SF0166 should be stored at 2–8°C and protected from light.

Throughout the study, the Investigator or designee will be responsible for the accounting of all IP. The Investigator must ensure that the IP are not used in an unauthorized manner.

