9.3 Concomitant Treatments

9.3.1 Permitted Treatments

Medications not specifically excluded in [Section 9.3.2](#) may be taken as necessary. For clarity, the following are permitted:

- Anti-VEGF injections for treatment of the non-study eye, including:
 - Eylea (aflibercept)
 - Lucentis (ranibizumab)
 - Avastin (bevacizumab)
 - Macugen (pegaptanib)
- Concomitant treatment with antibiotics at the discretion of the Investigator
- Artificial tears

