10.0 STUDY PROCEDURES

10.1 Visit 1 – Screening/Randomization

After obtaining written informed consent and Health Insurance Portability and Accountability Act (HIPAA) authorization, site staff will perform/assess the following in the order suggested below.

1. Each screened subject should be assigned a subject identifying number, based on the next available number in the eCRF.
2. Collect subject demographic information.
3. Collect ocular and non-ocular medical history.
4. Collect concomitant medications taken during the previous 12 months. Ask specifically about the use of Iluvien during the previous 36 months.
5. Administer UPT for female subjects of child-bearing potential.
6. Conduct in-office HbA1c test following test manufacturer guidelines.
7. Conduct the following ocular assessments on both eyes (refer to [Section 15.0](#) for further details):

- a. BCVA by ETDRS
- b. Slit-lamp Biomicroscopy
- c. IOP by Tonopen or Applanation
- d. Spectral Domain OCT
- e. Indirect Ophthalmoscopy/Dilated Fundus Examination
- f. Fundus Photography
- g. Fluorescein Angiography
8. Assess inclusion/exclusion criteria.
9. If subject is eligible, randomize the subject by entering information into the IWRS.
10. Dispense kit number provided by IWRS and provide dosing instructions/diary to the subject.
11. The first dose of study medication should be administered within the clinic under site staff supervision, and subsequent doses will be self-administered following the subject's visit.
12. Assess for any AEs occurring from the time of informed consent.
13. Provide instruction for the subject to:
 - a. Dose IP as instructed
 - b. Complete dosing information in subject diary.
 - c. Return for Visit 2 (Day 14) in 2 weeks (\pm 2 days).
14. Prepare and upload OCT images to the central reading center, and upload fundus photography to ShareFile.

Note: Subjects can be re-screened at the discretion of the Investigator if there is reasonable clinical evidence to suggest the subject may qualify after initial screen failure. The Investigator should contact the Sponsor to discuss re-screenings prior to conducting the visits.

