12.3 Classification, Relationship, and Intensity

Each AE will be classified as serious or non-serious using the definitions provided above.

The severity of each ae will be classified as mild, moderate, or severe using the following definitions:

- Mild: An AE is mild if the subject is aware of but can easily tolerate the sign or symptom.
- Moderate: An AE is moderate if the sign or symptom results in discomfort significant enough to cause interference with the subject's usual activities.
- Severe: An AE is severe if the sign or symptom is incapacitating and results in the subject's inability to work or engage in their usual activities.

The Investigator will review each event and assess its relationship to use of IP (unrelated, unlikely, possibly, probably, definitely). The AE will be assessed using the following definitions:

- Unrelated
 - Event occurring before dosing.
 - Event or intercurrent illness due wholly to factors other than IP use.
- Unlikely
 - Poor temporal relationship with IP use.
 - Event easily explained by subject's clinical state or other factors.
- Possible
 - Reasonable temporal relationship with IP use.
 - Event could be explained by subject's clinical state or other factors.
- Probable
 - Reasonable temporal relationship with IP use.
 - Likely to be known reaction to agent or chemical group, or predicted by known pharmacology.
 - Event cannot easily be explained by subject's clinical state or other factors.
- Definite
 - Distinct temporal relationship with IP use.
 - Known reaction to agent or chemical group, or predicted by known pharmacology.
 - Event cannot be explained by subject's clinical state or other factors.

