12.5 Procedures for Recording and Reporting

All AEs must be documented on the AE eCRF by the site and are monitored on a routine basis by the Sponsor. AEs are collected from the time of informed consent. Any pre-existing medical conditions or symptoms present in a subject are not considered AEs in the study unless there is a clinically significant worsening.

The Investigator must also promptly (i.e., within 24 hours of awareness) document all SAEs with details including the date of occurrence, severity, treatment (if applicable), outcome, and assessments of the seriousness and causality. The site must submit all available information on SAEs to the study Sponsor immediately as follows:

- All available information should be reported into the eCRF and on paper SAE form within 24 hours of becoming aware of the event.
- Document all relevant information from discharge summary, autopsy report, certificate of death, etc. (as applicable), in narrative section of SAE eCRF. Copies of this relevant source documentation should also be redacted and submitted to the Contract Research Organization (CRO), Lexitas Pharma Services, via fax.
- Additional relevant information after initial reporting is to be entered into the eCRF and on paper SAE form as soon as the data become available.
- Document any changes to concomitant medications on the appropriate eCRFs.

The Investigator must also report all SAEs to the IRB/IEC, according to the institution's requirements.

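### The only adverse-event summary specified is one undifferentiated any-AE percentage, which blurs a dose difference in a small trial with no vehicle arm

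*Combined protocol and SAP*

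**What the plan says.** Section 11.3.4 gives the AE method in two sentences. The first is "Adverse events will be summarized by presenting the number and percentage of subjects having any adverse event". The second is "Any other information collected (such as severity or relationship to investigational product) will be listed as appropriate". The statistical methods row of the synopsis says the same. Section 12.1 names four further safety parameters alongside AEs: BCVA, slit-lamp findings, fundus findings and IOP.

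Several other sections bear on what an unrestricted count takes in:

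- Section 12.5: "AEs are collected from the time of informed consent". Section 12.3 has a relationship class for an "Event occurring before dosing", so such events are recorded as AEs and rated unrelated.
- Section 10.1 puts consent, screening, randomization and dosing in one visit: "The first dose of study medication should be administered within the clinic under site staff supervision".
- Section 9.2 lets the investigator treat both eyes with SF0166 if both qualify. Section 9.3.1 permits "Anti-VEGF injections for treatment of the non-study eye".
- Section 8.0 sets 28 days on treatment and 28 days of follow-up. Sections 10.7 and 11.4 keep rescued subjects in follow-up to the end.

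No section defines a treatment-emergent AE or divides AEs by body site, by eye, by whether the eye was dosed, or by period.

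**The concern.** Safety is the first-named objective, and the synopsis justifies 20 subjects per arm as enough to tell the doses apart on efficacy and safety. There is no vehicle arm, so a difference between the two doses is the only randomized signal that an AE comes from the drug.

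The specified summary gives the same weight to a subject with one mild systemic event and a subject with a severe, definitely related reaction in a dosed eye. In a diabetic population, with fellow-eye injections and rescue injections both allowed, many counted events may have nothing to do with the dose. They raise both arms' percentages and pull them together. The five-level relationship scale and the three-level severity scale of Section 12.3, which would help to separate the two kinds of event, are collected but not tabulated. If grouping is left until the listings are read after unmasking, the groups will be chosen with the results in view.

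**Working it through.** **The plan's own figure.** The synopsis gives 20 per arm with no AE rate, difference, significance level or power. It can be neither reproduced nor contradicted. The question here is only what the specified summary does to a dose difference.

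**Inputs.** n = 20 per arm comes from the synopsis. The drug-related AE probabilities p and the background probability b are assumptions, because the documents give no AE rates. Background events are taken as equally likely in both arms and independent of drug-related events.

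**Formula.** P(any AE) = 1 − (1 − p)(1 − b). For two doses, the difference in any-AE probability is (1 − b)(p_high − p_low). The standard error of the difference is √[(q_low(1 − q_low) + q_high(1 − q_high))/20], where q is the any-AE probability. The ratio of difference to standard error is used only to describe how far the two percentages stand apart against sampling noise.

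**Result for p = 10% (low dose) and 30% (high dose).**

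| b | Low | High | Difference (points) | SE | Ratio |
|---|---|---|---|---|---|
| 0 | 10% | 30% | 20 | 0.122 | 1.63 |
| 0.02 | 11.8% | 31.4% | 19.6 | 0.126 | 1.55 |
| 0.10 | 19% | 37% | 18 | 0.139 | 1.29 |
| 0.30 | 37% | 51% | 14 | 0.155 | 0.90 |
| 0.50 | 55% | 65% | 10 | 0.154 | 0.65 |

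Example, b = 0.3: 1 − 0.9 × 0.7 = 0.37 and 1 − 0.7 × 0.7 = 0.51. The difference is 0.14, the SE is √[(0.2331 + 0.2499)/20] = 0.155, and the ratio is 0.90.

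**A larger assumed effect.** For 10% against 50%, the 40-point difference becomes 0.7 × 40 = 28 points at b = 0.3 and 0.5 × 40 = 20 points at b = 0.5. The proportional shrinkage is the same.

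**Does the standard error always grow?** No. For 50% against 70% with b = 0.5, the rates become 75% and 85%. The summed binomial variance falls from 0.25 + 0.21 = 0.46 to 0.1875 + 0.1275 = 0.315. The difference still halves, and the ratio falls from 0.20/0.152 = 1.32 to 0.10/0.125 = 0.80. Shrinkage of the difference is general; a larger standard error is not.

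**How much comes from the time before dosing?** Consent and first dose fall in the same visit, so this period is hours. Even at b = 0.02 for those hours, 20 points becomes 19.6. Any material b must come from systemic events, undosed-eye events or events after rescue.

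**The case against.** The strongest reply is that the AE percentage is one of five safety parameters. Slit-lamp examination grades bulbar injection, erythema, corneal edema, and anterior-chamber cells and flare (Section 15.2), in both eyes at every scheduled visit. IOP, fundus findings and BCVA follow the same schedule. Much local tolerability is therefore visible by eye and by visit outside the AE count. This stands, and it limits the point to AEs. It does not remove it: symptoms such as stinging are not graded slit-lamp items, and systemic effects would appear mainly as AEs.

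Second, the trial is descriptive, the AE rates above are assumed, and listings for about 40 subjects can be read by hand. This also stands. Even undiluted, the 10% against 30% example gives a ratio of only 1.63, so better tables would not make 20 per arm decisive.

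Third, not all pooled events are noise. Where both eyes receive SF0166, fellow-eye events reflect exposure, and delayed effects may appear after Day 28. Any split must therefore be by whether the eye was dosed, and follow-up events must be kept.

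Some stronger readings are tempting but unsupported:

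- A reader might infer a rule that both eyes and both periods are pooled. No such rule is written; pooling follows from an unrestricted count.
- A reader might infer that collection from consent distorts the comparison. The interval to first dose is too short for that.
- A reader might infer that severity and relationship will never be compared by dose. The plan lists them as appropriate and allows exploratory comparisons.
- A reader might infer lost power for a safety test. No formal test is planned.

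**Conclusion.** The point holds as one about AE tabulation. The sole specified AE summary is a single any-AE percentage, and it is a poor instrument for the between-dose safety comparison that the synopsis gives as a reason for the sample size. Dose-unrelated events reduce the visible difference by the factor (1 − b). On assumed rates of 10% and 30%, that means 14 of 20 points remain at b = 0.3 and 10 of 20 at b = 0.5; at b = 0.10, 18 remain and the loss is minor.

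This rests on background events being equally likely in both arms and independent of drug-related events. Events after rescue may not meet that condition, because the need for rescue could itself depend on dose; this is a reason to flag them rather than assume that they cancel. The true b is unknown.

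The harm is to descriptive interpretation of AEs and is partly offset by the other four safety parameters. The documents do not support saying that local tolerability cannot be assessed, or that the safety comparison as a whole fails. The change is still worth making, because it is cheap and fixes the groupings before unmasking.

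**What to change.** In Section 11.3.4 and the synopsis, keep the any-AE line. Add, by dose, the number and percentage of subjects with treatment-emergent AEs, defined as onset after the first dose, in separate one-way tables:

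- by site: ocular in dosed eyes, ocular in undosed eyes, and non-ocular;
- by period: on-treatment and post-treatment;
- by worst severity;
- by relationship: possible, probable or definite.

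Do not cross these fully. Three sites × two periods × three severities × two relationship groups would give 36 cells per dose for 20 subjects. List pre-dose events separately, and flag events after rescue or after a fellow-eye injection. The onset rule will not remove reactions to the fluorescein given again at Visit 3; those are best recognized from the relationship rating.

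Cost: a few extra tables, with no change in sample size or visits. Severity and relationship are already collected. AE onset date and affected eye must be on the AE eCRF, together with a record of which eyes were dosed. Because consent and first dose share a day, Day 0 events also need an onset time or a before/after-first-dose tick box.
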